1.3.2. Clinical Safety of Nivolumab

A total of 39 and 306 subjects with selected recurrent or treatment-refractory malignancies have been treated in a completed Phase 1 single-dose study (MDX1106-01) and a completed Phase 1 multidose study (CA209003 or MDX1106-03), respectively. As the safety profile from MDX1106-03 to date is consistent with that observed for MDX1106-01, only data from the larger and more recent study (MDX1106-03 or CA209003) is presented here.

A review of the safety data by tumor type (RCC, NSCLC, metastatic castration-resistant prostate cancer, colorectal cancer, and melanoma) did not show any clinically meaningful differences in the proportion of subjects with AEs noted across tumor types.

Overall, the safety profile of nivolumab monotherapy was generally manageable and was consistent with the mechanism of action of nivolumab. No MTD was reached at doses tested up to 10 mg/kg Q2W. The nature, frequency, and severity of any causality and treatment-related safety events were similar across tumor types.

The following were the key safety findings for the subjects in MDX1106-03 or CA209003

- Drug-related AEs (any grade) were reported in 75.2%, and drug-related Grade 3-4 AEs were reported in 17.0% of subjects.
- The most frequently reported drug-related AE was fatigue (28.1%). Other drug-related AEs Grade 3-4 reported in more than 2 subjects were pneumonitis (1.3%), lymphopenia (1.3%), diarrhea (1.0%), abdominal pain (1.0%), CD4 lymphocytes decreased (1.0%), and hypophosphatemia (1.0%).
- The most frequently reported drug-related SAE was pneumonitis (7 subjects, 2.3%). Drug-related Grade 3-4 pneumonitis was reported in 4 (1.3%).
- The most frequently reported drug-related select AE categories (any grade) were skin (24.5%), GI (14.1%), and endocrine (9.5%).
- AEs belonging to the pulmonary and renal select AE categories were unexpected, drug-related toxicities associated with the use of nivolumab.
- AEs belonging to select AE categories were generally manageable and reversible with the use of immunosuppressants.

Deaths

The majority of the deaths were due to disease progression. Three subjects (1.0%) died due to study drug toxicity at the time of database lock; 2 out of 3 subjects died within 100 days of last dose of nivolumab, and 1 died > 100 days after the last dose of nivolumab. The reported causes of death for these 3 subjects were:

- Non-drug-related cardiopulmonary arrest due to complications from Grade 5 sepsis (drug-related)
- Drug-related sepsis
- Drug-related respiratory failure secondary to pneumonitis and progressive disease

After database lock for the final CSR, 2 subjects were reported to have died; both were subjects with NSCLC treated with 3-mg/kg nivolumab. The reported causes of death for these 2 subjects were:

- Drug-related pneumonitis
- Non-drug-related infection after experiencing drug-related Grade 3 pneumonitis

Although not considered to be the primary cause of death in all 5 subjects described above, pneumonitis was considered a contributory factor in each case.

Preliminary new non-clinical safety findings of adverse pregnancy outcomes and infant losses in the absence of overt maternal toxicity have been reported. The findings of increased late stage pregnancy loss and early infant deaths/euthanasia in nivolumab exposed pregnant monkeys suggest a potential risk to human pregnancy if there is continued treatment with nivolumab during pregnancy.

Additional details on the safety profile of nivolumab, including results from other clinical studies, are also available in the BMS-936558 (nivolumab) Investigator Brochure (IB).

Adverse Event Management Algorithms

Because of the potential for clinically meaningful nivolumab-related AEs requiring early recognition and prompt intervention, management algorithms have been developed for suspected pulmonary toxicity, gastrointestinal, hepatotoxicity, endocrinopathy, skin toxicity, neurological toxicity, and nephrotoxicity.

The algorithms recommended for utilization are contained in Section 8 of the protocol.

1.3.3. Clinical Efficacy of Nivolumab

In CA209003 (MDX1106-03), the clinical activity of nivolumab was demonstrated in various tumor types and across a range of doses (0.1 mg/kg, 0.3 mg/kg, 1 mg/kg, 3 mg/kg, 10 mg/kg).

For monotherapy in NSCLC, the overall objective response rate was 17%; the most active doses were 3 mg/kg and 10 mg/kg. Only a single response was reported at 1 mg/kg. Responses were observed in subjects with NSCLC (both squamous and nonsquamous subtypes) with a median duration of response of 17 months. A summary of ORR, progression-free survival rate (PFSR), and overall survival (OS) rate for NSCLC subjects by histology is provided in the Investigator's Brochure.

For melanoma subjects who were administered nivolumab monotherapy Q2W at doses ranging from 0.1 mg/kg to 10 mg/kg, the ORR was 31% (N = 107). The majority of responses were durable and exceeded 6 months. A summary of ORR, PFSR, and OS rate for subjects with melanoma is provided in the Investigator's Brochure.

The ORR was 21% (N = 34) for RCC subjects who were administered nivolumab monotherapy Q2W at doses of 1 mg/kg or 10 mg/kg. The majority of responses were durable and exceeded 6 months. A summary of ORR, PFSR, and OS rate for subjects with RCC is provided in IB.

Results from a Phase I study including 29 patients with B-NHL showed activity of nivolumab in patients with relapsed DLBCL and FL (Lesokhin 2014).³³ The patients were heavily pretreated including prior autologous transplant and > 3 lines of prior chemotherapy. The total number of patients with DLBCL was 11, CR is reported in 1 (9%), PR in 3 (27%), and SD in 3 (27%) of patients with PFS of 24% at 24 weeks. The total number of patients with FL in the study was 11; CR was reported in 1 (10%), PR in 3 (30%), SD in 6 (60%) of patients with PFS of 24% at 24 weeks.

1.4. Overall Rationale for the Study

Unpublished data obtained in a model of A20 murine B-cell lymphoma tumors xenografted onto immune-competent BALB/C mice indicate a potent and synergistic anti-tumor efficacy of a combination treatment of ibrutinib and an antibody against the murine PD-1 ligand PD-L1. It is of importance that the enhanced anti-tumor efficacy of the ibrutinib and anti-PD-L1 antibody combination treatment was observed in a lymphoma model resistant to ibrutinib monotherapy.

These experimental data give rise to separate scientific hypotheses:

- a. The PD-1/PD-L1 axis is a mechanism of intrinsic or acquired resistance to ibrutinib in tumors otherwise sensitive to its inhibitory activity and/or
- b. Ibrutinib has immune-modulatory activity potentiating the anti-tumor activity of PD-1/PD-L1 immune checkpoint inhibition.

Recent data have shown that the tumor microenvironment plays an important role in the clinical course of the disease and the outcome of patients with NHL. Lymph nodes in patients with NHL contain not just malignant B cells but normal immune cells including T cells, intratumoral macrophages, monocytes, dendritic cells, and natural-killer cells (Ansell 2013).² Although this tumor microenvironment supports the growth and survival of malignant B cells, the malignant B cells also define the constitution of the tumor microenvironment. The composition of this microenvironment and the presence of specific immune cells have prognostic significance for patients with FL (Dave 2004; Richendollar 2011).^{13,46} In addition, expression data obtained from biopsies of NHL patients indicate that malignant B cells modulate immune surveillance by driving the differentiation and function of intratumoral T cells (Ansell 2013).² Malignant B cells have been found to express multiple ligands responsible for inducing regulatory T cells (Treg cells) and suppressing intratumoral effector T cells.

Of particular interest is the interaction between the PD-L1, a member of the B7 family (B7-H1) of co-stimulatory molecules which is frequently over-expressed on malignant B-cells (Richendollar 2011)⁴⁶ and its cognate receptor PD-1, a member of the CD28 receptor family, expressed on activated, effector T-cells. In CLL, overexpression of both PD-1 and PD-L1 has been detected (Grzywnowicz 2012)²² while PD-1 expression appears to be of importance in FL (Carreras 2009).⁸ The PD-1/PD-L1 interaction between malignant B-cells and effector T-cells results in a suppression of the cellular immune response directed against the malignant B-cells. This suppression occurs through decreased induction of various cytokines, decreased expression of T-cell survival proteins, impaired cytotoxic capabilities and most through a direct inhibition of the proliferation of activated T-cells (Gzywnowicz 2012).²² PD-1/PD-L1 thereby attenuates the T-cell response, leading to “T-cell exhaustion” and the maintenance of peripheral immune tolerance in lymphoma (Chen 2013; McClanahan 2012).^{11,34}

Ibrutinib has Immunomodulatory Activity in Lymphoma

Bruton’s tyrosine kinase, the molecular target of ibrutinib, is a member of the non-receptor TEC-kinase family, which also includes the structurally homologous tyrosine-protein kinase (TEC), the IL2-inducible T cell kinase (ITK) and the endothelial/epithelial tyrosine kinase BMX/ETK.

Intracellular tyrosine kinase is active in T-cell malignancies and has been linked to tumor immune evasion and survival through its critical role in T-helper type 2 (Th2) cell differentiation (Dubovsky 2013).¹⁷ Recent experimental data demonstrate that ibrutinib, in addition to blocking BTK, also irreversibly binds to ITK. In relevant in vitro and in vivo models, ibrutinib inhibited ITK-mediated downstream activation of T-cell receptor (TCR) stimulation in Th2 polarized CD4-T helper cells. Th1 cells were not affected possibly because they express a kinase that can compensate for loss of ITK signaling. Consistent with these findings, a blocking of Th2 cell activation and dominance of a Th1-profile was induced upon ibrutinib exposure of CD4 T-cell populations isolated from CLL patients in vitro (Dubovsky 2013).¹⁷ Similarly, a Th-1 skewed cytokine pattern was detected in clinical samples obtained from ibrutinib treated CLL patients (Dubovsky 2013; Niemann 2013).^{17,35} It has been proposed that the stimulation and expansion of

Th2 polarized CD4 T-cells constitutes a specific molecular mechanism of immune evasion observed in solid tumors and leukemias (Dubovsky 2013).¹⁷

This identification of ibrutinib as an inhibitor of ITK-mediated TCR signaling in Th2-polarized CD4-T-cells may address and reverse this specific molecular mechanism. In consequence, the therapeutic activity of ibrutinib as a single-agent immunomodulator or in combination with T-cell based cancer immunotherapies (Dubovsky 2013)¹⁷ including antibodies targeting the PD-1/PD-L1 axis should be explored.

2. OBJECTIVES AND HYPOTHESIS

2.1. Objectives

Primary Objective

Part A (Dose Optimization Cohorts): The primary objective of Part A is to determine whether ibrutinib and nivolumab can be safely combined and to establish the recommended Phase 2 dose (RP2D) for this combination in subjects with hematological disorders.

Part B (Expansion Cohorts): The primary objective of Part B is to determine the preliminary activity of the ibrutinib/nivolumab combination regimen in subjects with relapsed/refractory CLL/SLL and poor prognosis (deletion 17p or deletion 11q), relapsed/refractory FL, relapsed/refractory DLBCL, or Richter syndrome in comparison to historical results.

Secondary Objectives

The secondary objectives are:

- To evaluate the safety profile of the ibrutinib and nivolumab combination regimen
- To assess overall response rate (ORR), duration of response, duration of stable disease, progression-free survival rate at 1 year, and overall survival at 1 year of the ibrutinib and nivolumab combination regimen
- To characterize and explore the pharmacokinetic profile of ibrutinib and nivolumab compared with existing single-agent treatment data; and the potential relationships between ibrutinib and nivolumab metrics of exposure with relevant clinical or biomarker information (Part A and B)

Exploratory Objectives

- To characterize the molecular effects of the ibrutinib and nivolumab combination regimen on tumor cells and the immune response; and identify biomarkers of response or resistance to the combination
- To evaluate the immunogenicity of nivolumab

2.2. Hypothesis

In Part A (Dose Optimizations), the study will evaluate and describe whether ibrutinib, administered at daily oral doses between 420 mg and up to 560 mg, can be safely combined with

nivolumab 3 mg/kg administered IV every 2 weeks such that $\leq 30\%$ of subjects with CLL/SLL or NHL experience a DLT.

In Part B (Dose Expansion; Cohorts B1, B2, B3, and B4), the study will evaluate and describe whether ibrutinib combined with nivolumab can result in an overall response rate of more than 20%.

[figure not shown]
3. STUDY DESIGN AND RATIONALE

3.1. Overview of Study Design

This is an open-label Phase 1/2a study, which consists of Part A (Dose Optimization Cohorts) and Part B (Expansion Cohorts). In the context of this study, a treatment ‘cycle’ is defined as a course of treatment of 14 days starting with the intravenous administration of nivolumab on Day 1 of each cycle along with once daily oral intake of ibrutinib on all days.

It is anticipated that approximately 158 subjects will be enrolled throughout the study; up to 18 subjects in the dose optimization period (Part A) and approximately 140 subjects during the expansion period (Part B).

Figure 1: Study Design Overview

Part A (Dose Optimization Cohorts) is designed to determine the RP2D for the combination based on safety, pharmacokinetic, and pharmacodynamic assessments. Two dose optimization cohorts will be explored, applying the Modified Toxicity Probability Interval (mTPI) design to evaluate subjects with relapsed/refractory CLL/SLL or B-NHL.

Part B (Dose Expansion Cohorts) will be open for enrollment after the RP2D is determined in Part A. In Part B, further assessment of the RP2D will be explored in 3 subject populations to further evaluate the safety and clinical activity of ibrutinib in combination with nivolumab. During the expansion period, subjects with CLL/SLL with del 17p or 11q (Cohort B1), FL (Cohort B2), DLBCL (Cohort B3), and Richter syndrome (Cohort B4) will be enrolled. Approximately 35 subjects will be enrolled in each of the expansion cohorts. The subjects will be treated at the RP2D level selected to further assess the safety, pharmacokinetics, pharmacodynamics, pharmacogenomics, and activity of the combination.

Part A and Part B of the study will be divided into 3 periods:

- Screening Period: pretreatment screening period of up to 28 days before enrollment
- Treatment Period: open-label treatment period ending at the End-of-Treatment Visit
- Follow-up Period: posttreatment follow-up period until the end of study (when all subjects have completed the End-of-Treatment Visit). Refer to [Table 1](#) for a complete list of procedures to be performed during the study.

During the Treatment Period, all subjects will be closely monitored for safety. Toxicities (AEs and laboratory abnormalities) will be evaluated and graded according to the National Cancer Institute Common Terminology Criteria for Adverse Events (NCI CTCAE Version 4).

Preliminary activity and clinical response will be evaluated every 5 cycles for the first 15 months, thereafter every 12 cycles until progression, at the end of treatment, and every 6 months in follow-up, in the event the subject has not progressed while on therapy and did not start subsequent therapy. Lymphoma including Richter syndrome will be evaluated for response according to the Lugano Classification (Cheson 2014);¹² CLL will be evaluated according to International Workshop on Chronic Lymphocytic Leukemia (IWCLL) (Hallek 2008), see Section 10.1.²³ Identical methodology should be used for disease assessment at baseline and throughout the course of the study.

Subjects will be assigned to receive oral daily doses of ibrutinib (self-administered) in combination with intravenous nivolumab on Day 1 of each cycle starting from Dose Level 1 ([Table 4](#)). In Cohort B1 and B2, to assess pharmacokinetic and pharmacodynamic characteristics of ibrutinib monotherapy, ibrutinib will be given at the recommended Phase 2 dose over an initial period of seven days prior to the first dose of nivolumab (Day -7 to -1). Refer to the Dosage and Administration schedule (Section 6) for further detail. Protocol specified treatment modifications for ibrutinib and nivolumab will be implemented as necessary (Section 6.4). Additional dosing or schedule changes for ibrutinib or nivolumab can be requested by the Study Evaluation Team (SET) based on preliminary clinical data during dose optimization. Doses may be held or reduced based on the severity of and the recovery from previous toxicity. Dose re-escalation may be allowed after

recovery from toxicity following consultation with the Sponsor. In Part A intra-patient dose escalation may be requested by the investigator and discussed with the medical monitor once a subsequent higher combination dose has been declared acceptable by the SET for subjects who (1) have received at least 4 cycles of combination treatment at the assigned dose level, and (2) have not experienced a DLT or therapy-related SAE. Subjects whose dose has been escalated will not be considered for the safety evaluation in the subsequent dose level and the determination of the RP2D.

The study treatment will be continued until:

- documented confirmed disease progression (except in cases of clinical improvement/stability; see Section 11.2)
- unacceptable toxicity
- intercurrent illness that prevents further administration of treatment
- subject refuses further therapy
- investigator's decision to withdraw the subject
- pregnancy of the subject
- noncompliance with study treatment or procedure requirements

The average duration of study therapy is expected to be approximately 6 months.

In Part A of the study, a SET, consisting of the principal investigators, sponsor medical monitors, and the sponsor's clinical pharmacologist, or their designees, and the sponsor statistician will review all available data upon completion of the first 2 treatment cycles (ie, 4 weeks of study therapy) for all subjects at each dose cohort to determine DLTs, if dose escalation is acceptable, and ultimately to determine the recommended Phase 2 dose.

In Part B of the study, all subjects in each cohort may be evaluated for response by the SET and additional functional representatives from Janssen, as applicable. The SET along with optional other internal members may review safety on an ad hoc basis, and efficacy endpoints (including but not limited to ORR).

The End-of-Treatment Visit will occur within 30 days after the last dose of ibrutinib or nivolumab, whichever treatment occurred last.

During the Follow-up Period, long-term safety, survival status, disease progression, subsequent anticancer therapy, and occurrence of other primary malignancy data will be collected as well as anti-drug antibody (ADA) sampling if applicable. During the Follow-up Period, subjects should be followed for safety up to 30 days after the last dose of ibrutinib or 100 days after the last nivolumab infusion, whichever is later. The safety follow-up includes adverse event reporting and laboratory assessments (at the first follow-up). Thereafter, follow-up visits will be completed approximately every 3 months until death or the end of study. Subjects who have developed treatment-related Grade 3 or higher toxicity at the end of treatment will be assessed until recovery to Grade ≤ 1 or baseline, deemed irreversible, or until end of study. Adverse events leading to

discontinuation will be followed up until resolution or return to baseline, or end of study, whichever occur first.

The primary analysis of the study will be performed 6 months after the last subject has received the first dose of study medication, or earlier if that subject discontinues study therapy. After the cutoff for primary analysis, subjects who are receiving study treatment can continue treatment per protocol until progression, unacceptable toxicity, withdrawal of consent, or other reason as listed in Section 11.2. End of study is defined as the last subject who completed the EOT Treatment assessment.

After the clinical cutoff at a minimum the following data will be collected on eCRF: SAEs and AEs Grade ≥ 3 , laboratory assessments (Grade ≥ 3 or clinically significant), efficacy, survival status, and treatment administration. Data collected from the primary analysis until end of study will be summarized in a clinical study report addendum.

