and stem cells have already transformed the standard-of-care in selected hematologic malignancies and solid tumors. More recently, major clinical progress has been observed with active immunotherapies addressing molecular mechanisms of evasion of immune-mediated tumor destruction. Multiple therapeutic approaches are currently being pursued to overcome the immune-tolerance of tumors (Drake 2014).¹⁵ Of these the blockade of immune-checkpoint receptor-ligand interactions between tumor cells and tumor-specific T-lymphocytes (Drake 2014)¹⁵ has emerged as the most promising novel therapy. Among the immunotherapies targeting immune-checkpoints, antibodies directed against the PD-1 receptor expressed on tumor-specific T-lymphocytes such as nivolumab, have demonstrated astonishing single-agent efficacy in patients with advanced melanoma, renal cell cancer (RCC), non-small-cell lung cancer (NSCLC) and other solid tumor indications (Robert 2013; Dranoff 2013; Sznol 2013).^{47,16,52} Limited clinical data also indicate activity of anti-PD 1 antibody therapy in patients with hematologic malignancies (Brody 2011; Shi 2013)^{7,50} suggesting a very broad clinical potential for specific immune check point inhibitors (Robert 2013; Sznol 2013).^{47,52} Clinical studies are underway to further investigate the efficacy of PD-1 immune check-point inhibition in hematologic malignancies (Armand 2013).³

Pre-clinical data obtained in relevant tumor models as well as early clinical data indicate that due to the different mode-of-action, anti-proliferative therapies targeting oncogenic signal-transduction pathways can be safely combined with antibody-mediated PD-1 immune-checkpoint blockade (Sznol 2013).⁵² More importantly, based on the different onset of clinical activity, which is often early with signal-transduction inhibitors and frequently delayed with immune-checkpoint inhibitors, these treatments may ultimately complement one another, leading to a more pronounced anti-tumor activity in sensitive tumor indications (Sznol 2013).⁵²

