In a Phase 3 randomized, comparator-controlled, pivotal study in subjects with CLL/SLL (Study 1112), ibrutinib improved efficacy outcomes in subjects with previously treated CLL/SLL compared to that ofatumumab. Analysis of PFS (per the Independent Review Committee [IRC]) demonstrated a statistically significant reduction in the risk of disease progression or death in the ibrutinib arm compared to the ofatumumab arm (HR=0.215, $p<0.0001$). Analysis of OS showed that subjects in the ibrutinib arm had a statistically significant reduction in the risk of death (HR=0.434, $p=0.0049$). The ORR (IRC assessment) was significantly higher ($p<0.0001$) for subjects in the ibrutinib arm (42.6%) than those in the ofatumumab arm (4.1%). The ORR, when including partial response with lymphocytosis (PR-L) (per IRC assessment), was 62.6% for the ibrutinib arm and 4.1% for the ofatumumab arm ($p<0.0001$).

Follicular Lymphoma (FL)

In the Phase I study PCYC-04573, sixteen subjects enrolled to the dose-escalation phase had a diagnosis of FL (Fowler 2012).¹⁸ Eleven subjects received ibrutinib at doses that achieved full BTK occupancy (ie, 2.5 mg/kg or higher). Median time on ibrutinib was 7 months (0 to 29 months) and time to response was 4.6 months. Overall response rate was 54.5% (3 CRs, 2 PRs). Responses were durable (median response duration: 12.3 months). Three patients had chemorefractory disease; 2 of these patients responded (1 CR, 1 PR). On the basis of these very encouraging early efficacy data the single-arm, multicenter Phase 2 study PCI-32765FLR2002 was initiated.

Diffuse Large B-cell Lymphoma (DLBCL)

In a Phase 2 study of ibrutinib in subjects with DLBCL (Study 1106), an interim analysis of response in DLBCL showed an ORR of 25% (CR 9% and PR 16%) with a median time on study of 3.9 months. An analysis of response by molecular subtype demonstrated that subjects with molecular subtype activated B-cell-like (ABC) (non-germinal-cell B-cell-like [GCB]) had an ORR of 41% (CR 17% and PR 24%) and among subjects with the GCB subtype, ORR was 5% (CR 0% and PR 5%).

Richter syndrome

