1.2. Trial Design

This is an open-label Phase 1/2a study, which consists of Part A (Dose Optimization Cohorts A1 and A2) and Part B (Expansion Cohorts B1, B2, B3 and B4). In the context of this study, a treatment 'cycle' is defined as a course of treatment of 14 days starting with the intravenous administration of nivolumab on Day 1 of each cycle along with once daily oral intake of ibrutinib on all days.

It is anticipated that approximately 158 subjects for both Parts A and B would be enrolled.

Part B (Dose Expansion Cohorts) will be open for enrollment after the RP2D is determined in Part A. In Part B, further assessment of the RP2D will be explored in 4 subject populations to further evaluate the safety and clinical activity of ibrutinib in combination with nivolumab. During the expansion period, subjects with CLL/SLL with del 17p or 11q (Cohort B1), FL (Cohort B2), DLBCL including FL transformed into DLBCL (transformed DLBCL) (Cohort B3), and Richter syndrome (Cohort B4) will be enrolled. Approximately 35 subjects will be

enrolled in each of the expansion cohorts. The subjects will be treated at the RP2D level selected to further assess the safety, pharmacokinetics, pharmacodynamics, pharmacogenomics, and activity of the combination.

The median duration of study therapy is expected to be approximately from 2 (DLBCL) to 15 (CLL) months.

The End-of-Treatment Visit will occur within 30 days after the last dose of ibrutinib or nivolumab, whichever treatment occurred last.

During the Follow-up Period, long-term safety, survival status, disease progression, subsequent anticancer therapy, and occurrence of other primary malignancy data will be collected. During the Follow-up Period, subjects should be followed for safety up to 30 days after the last dose of ibrutinib or 100 days after the last nivolumab infusion, whichever is later. The safety includes adverse event reporting and laboratory assessments (at the first follow up). Thereafter Follow-up visits will be completed approximately every 3 months until death or the end of study. Subjects who have developed treatment-related Grade 3 or higher toxicity at the end of treatment will be assessed until recovery to Grade ≤ 1 or baseline, deemed irreversible, or until end of study. Adverse events leading to discontinuation will be followed up until resolution or return to baseline, or end of study, whichever occur first.

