4. EFFICACY

The primary population for the primary efficacy endpoint, ORR, is the all-treated. Sensitivity analysis will be performed on the response-evaluable population, if deemed necessary. Unless otherwise specified efficacy analyses will be based on the all-treated population.

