4.1.3. General Analysis Considerations

For this study and its CSR, analyses of disease response and disease progression are based on investigator assessments. These assessments are based on IWCLL [International Workshop on Chronic Lymphocytic Leukemia (Hallek 2008)] for CLL patients and the Lugano Classification by Cheson (2014) for SLL, FL, DLBCL and Richter syndrome and using data collected at the clinical cutoff. Detailed criteria for response category can be found in Section 10.1 of the protocol. All the additional data collected after the clinical cutoff will be summarized in the CSR addendum.

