4.2. Primary Efficacy Endpoint(s)

4.2.1. Definition

The primary endpoint is ORR, defined as the proportion of subjects who achieve partial response or better [PR(+L) or better], as assessed by the investigators at or prior to initiation of subsequent anti-cancer therapy. The primary efficacy analysis of ORR will be conducted at performed 6 months after the last subject has received the first dose of study medication, or earlier if that subject discontinues study therapy. The analysis will be based on the all-treated population.

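### One subject stopping treatment can bring the primary ORR cutoff forward while other recent enrollees have had no scan or only one, which can lower the primary ORR of a late-accruing cohort

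*Protocol*

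**What the plan says.** Protocol 3.1 sets the primary analysis at "6 months after the last subject has received the first dose of study medication, or earlier if that subject discontinues study therapy". The same rule stands in the Protocol Synopsis and in SAP 1.2, 4.2.1 and 7.5. SAP 4.2.1 ties it directly to the primary endpoint: "or earlier if that subject discontinues study therapy. The analysis will be based on the all-treated population". SAP 4 confirms the population: "The primary population for the primary efficacy endpoint, ORR, is the all-treated". SAP 4.1.3 bases the response analyses on investigator assessments, "using data collected at the clinical cutoff". What comes later is reported separately: "Data collected from the primary analysis until end of study will be summarized in a clinical study report addendum".

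Two places differ. Protocol 11.1 gives the time of the primary analysis as 6 months after the last patient's first dose and has no early clause. Protocol 12.4 calculates ORR on the response-evaluable population, which the SAP keeps as a sensitivity analysis.

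The documents expect some short treatment and some late responses. SAP 1.2: "The median duration of study therapy is expected to be approximately from 2 (DLBCL) to 15 (CLL) months". Protocol 3.1 expects about 6 months on average. Protocol 1.1 describes activity as "often early with signal-transduction inhibitors and frequently delayed with immune-checkpoint inhibitors". For ibrutinib in follicular lymphoma, Protocol 1.2.4 reports that "time to response was 4.6 months".

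**The concern.** A 6-month minimum lets every subject pass the first two scheduled scans before ORR is computed. The early clause removes that minimum for everyone when one subject, the last enrolled, stops therapy. The clause does not say how much earlier the cutoff may be, and nothing else in the documents protects subjects enrolled shortly before.

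Best response can only stay the same or improve with longer observation. The all-treated denominator is fixed, and SAP 4.1.2 does not impute missing values. A subject without a scan therefore stays in the denominator with no response. An earlier cutoff can then only lower the expected primary ORR or leave it unchanged. What is at stake is the comparison with 20% in whichever cohort is still filling: an active combination could look weaker for a reason that has nothing to do with the drugs.

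**Working it through.** **1. The plan's own figure.** Protocol 12.3 and SAP 1.4 use ORR 20% versus 38%, one-sided alpha 0.1, power at least 0.8, and 32 evaluable of 35 enrolled. Exact binomial, n = 32, success at 10 or more responses: alpha 0.090, power 0.833. This reproduces 32 (n = 31 gives power 0.799). For all 35 treated, success at 11 or more: alpha 0.075, power 0.835. That is the reference with full follow-up.

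**2. Scan times.** Table 1 has CT every 5 cycles from Cycle 5, with 14-day cycles. Cycle 5 Day 1 is day 4 × 14 + 1 = 57 (8 weeks in). Cycle 10 Day 1 is day 9 × 14 + 1 = 127 (18 weeks in). In B1 and B2 the 7-day run-in makes both about a week later, counted from first ibrutinib.

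**3. Chance that the clause is triggered.** Assumption: exponential time on therapy. P(stop before t) = 1 − 2^(−t/median), or 1 − exp(−t/mean). Week 8 is 56/30.4375 = 1.84 months.

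| Time on therapy | Before 6 months | Before week 8 |
|---|---|---|
| Median 2 months (SAP, DLBCL) | 1 − 2^(−3) = 88% | 47% |
| Mean 6 months (Protocol) | 1 − e^(−1) = 63% | 26% |
| Median 15 months (SAP, CLL) | 1 − 2^(−0.4) = 24% | 8% |

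**4. Effect on a cohort still enrolling.** The documents give neither accrual nor response timing, so this is an illustration. Assumptions: 35 subjects enrolled evenly over 26, 52 or 78 weeks; true ORR 38%; a share f = 0.50 to 0.75 of responses seen at week 8 and the rest at week 18; cutoff on the day the last subject stops.

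Expected ORR = 0.38 × (subjects with both scans + f × subjects with one scan) / 35. Power is the exact probability of 11 or more documented responses. With 26-week accrual and a stop at week 4, 16 subjects have both scans, 13 have one and 6 have none: 0.38 × (16 + 0.5 × 13)/35 = 24.4%, and with f = 0.75, 28.0%.

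| Accrual | Stop at | No scan / one scan | Expected ORR | Power |
|---|---|---|---|---|
| 26 weeks | week 4 | 6 / 13 | 24–28% | 21–38% |
| 52 weeks | week 4 | 3 / 7 | 31–33% | 54–64% |
| 78 weeks | week 4 | 2 / 5 | 33–35% | 65–71% |
| 26 weeks | week 8 | 0 / 14 | 30–34% | 51–70% |
| 52 weeks | week 8 | 0 / 7 | 34–36% | 70–77% |
| 78 weeks | week 8 | 0 / 5 | 35–37% | 74–79% |
| any | week 26 | 0 / 0 | 38% | 84% |

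**5. Response-evaluable set.** For a stop at week 4, drop the unscanned subjects. Expected ORR is 30–34% on 29 subjects (26 weeks), 34–36% on 32 (52 weeks) and 35–37% on 33 (78 weeks). The bias is smaller, but evaluable n can fall below the planned 32, and any ordinary non-evaluability comes on top.

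**6. Sensitivity to response timing.** Assume 12-month accrual and responses recorded at the next scheduled scan. With an exponential 4.6-month median time to response, 78% of eventual responses are documented at a 6-month cutoff, 59% at 2 months and 53% at 1 month. With the 1.8-month CLL/SLL median in Protocol 1.2.4, or with responses required to arise before an exponential stop of therapy (2-month median), the shares are about 96–98%, 85–89% and 77–82%. The direction is stable; the size is not.

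**The case against.** The strongest reply is that nothing is lost. Under Protocol 3.1 efficacy data are still collected after cutoff, Table 1 continues scans, and late responses go into the addendum. A reader might infer that response follow-up ends for other subjects; the documents do not support that. A reader might also take the trigger to be dropout. It is stopping study therapy, and Protocol 11.2 says that this is not automatic withdrawal from the study. What stands of the concern is narrower: late responses miss the primary ORR.

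Second, large losses come from pairing the DLBCL time on therapy with the follicular lymphoma time to response. Those are different diseases, and the 4.6 months comes from a small dose-escalation subset and is not stated to be a median. Responses also cannot go on arising at that pace if half the subjects have stopped by 2 months. This is right. The 78% to 59% or 53% series is not a usable estimate, and even there the 22% missed at 6 months is not due to the clause.

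Third, one might infer bias in 1-year PFS and OS. These are Kaplan-Meier estimates with censoring, and a 6-month minimum does not cover one year either. An earlier cutoff costs precision; no bias is shown.

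Fourth, the study is non-randomised and largely descriptive, tests are conditional in SAP 4.1.1, and the error is conservative: it cannot create a false claim of activity. That limits the weight of the point but does not justify letting one patient set the follow-up.

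**Conclusion.** The point holds in a limited form. An early trigger biases the SAP's primary ORR downward or leaves it unchanged, and only in cohorts with subjects enrolled in the last months. Cohorts that finished accrual more than 6 months earlier keep at least the planned follow-up. On the Protocol's response-evaluable set the bias is smaller, with a possible shortfall below 32.

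The trigger is plausible in any disease and likely in DLBCL (24% to 88% before 6 months, exponential assumption). The size depends on unstated accrual and response timing. In the week-4 illustration expected ORR is 3 to 14 percentage points below 38%, worst with fast accrual. Power here refers to the one-sided 0.1 of the sample size; SAP 4.1.1 names 0.025, a separate matter. The documents do not show whether the clause was triggered, so no conclusion about reported results follows.

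**What to change.** Delete the early clause in the Protocol Synopsis and Section 3.1 and in SAP 1.2, 4.2.1 and 7.5, so that the cutoff is 6 months after the last subject's first dose, as Protocol 11.1 already reads. If an earlier cutoff is wanted, allow it only when all subjects with less than 6 months of follow-up have progressed, died, withdrawn or started subsequent therapy.

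No change in sample size is needed. Database lock may be up to a few months later than under an early trigger, but never later than the 6 months already planned. The Amendment 7 entry says that the primary objectives have already been analysed and published. For this trial, the practical step is to state in the report whether the early clause was used and to show each cohort's minimum follow-up, with the addendum ORR beside the primary ORR. The wording change then matters mainly for plans built on this one.
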